Component 2: Integrated Obesity Care. Families will receive evidence-based weight management treatment consistent with Stage 3 AAP Expert Committee Recommendations and United States Preventive Services Task Force (USPSTF) guidelines,^{8,47} tailored to the needs of each family. Treatment will include biweekly telehealth or in-person (included based on parent and healthcare stakeholder feedback) visits with members of an existing and established transdisciplinary group of obesity specialists (medical provider, psychologist, exercise physiologist, dietitian, and community health worker) from the Nemours Healthy Weight and Wellness Clinic, with an interpreter available for families whose preferred language is Spanish. Telehealth visits will be delivered via the Nemours App and in-person visits will be provided at Nemours Children's Health, Milford. Care provided will include motivational interviewing to establish lifestyle behaviors goals specific to each child's needs but following evidence-based lifestyle recommendations like MyPlate and the Traffic Light Diet, cognitive-behavioral strategies such as self-monitoring and stimulus control, positive parenting strategies, and management of child mood and self-esteem. Based on feedback from parent partners and in recognition of the challenges with attending biweekly visits, providers will reach out to parents by their preferred method of communication (App, phone, or text) if a family misses a visit. This outreach will focus on evaluating progress with lifestyle behavior goals, problem-solving strategies to assist with lifestyle behavior goals, setting new lifestyle behavior goals as appropriate, and ensuring families are connected to community programs as needed.

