
AIMS 2 and 3: EXAMINE IMPACT OF MICCO ON FAMILY ENGAGEMENT AND CHILD ADIPOSITY AND DISPARITIES IN THESE OUTCOMES

PARTICIPANTS: 184 families of children with obesity (BMI percentile $\geq 95^{\text{th}}$ percentile for age) ages 4-12 years who are patients of the primary care practices in Milford, Seaford, or Millsboro serving primarily rural populations will be identified from the EHR and with advertisement at community centers. Participants identified from the EHR will be contacted by text and/or e-mail message. Interested participants will be advised to contact a research team member, who will then contact interested families to assess eligibility criteria and interest in participation. If a family is eligible and interested after this contact, the research team member will arrange a time to conduct an informed consent process with the participant, who will sign an electronic consent.

STUDY DESIGN: Enrolled families will be randomly allocated to receive MICCO (see C.3) or an active control condition (standard care) using a 1:1 randomization scheme stratified by race/ethnicity (three groups impacted most by obesity in the community: Latino, non-Hispanic Black, non-Hispanic White; Figure 6). The intervention will be delivered over 6 months.

STANDARD CARE: An active control condition was selected to demonstrate the impact of the intervention beyond the typical care that a child would receive in primary care. Standard care will include bimonthly in-person visits for lifestyle counseling with the child's PCP per 2023 AAP Clinical Practice Guidelines.⁴⁷ PCPs will receive training on these recommendations at the start of the clinical trial, with refresher training provided every six months and a lifestyle handout provided to facilitate education at each nursing visit. PCPs will not be trained on MICCO. Only participants in the MICCO group will have access to the MICCO dashboard on the Nemours App to prevent contamination.

OUTCOME MEASURES

Family Engagement in Treatment: Study visits will be documented in the EHR as part of routine clinical care for all patients, including the number of visits with primary care providers (where obesity and lifestyle counseling was provided, per ICD-10 codes) or obesity specialists (including type of specialist) and number of cancelled/missed visits. Attrition (non-attendance to 6 month follow-up visit) will be assessed via EHR review. In addition, number of days in study will be assessed as a secondary outcome.

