on prior studies,¹¹⁻¹² we would need to enroll 184 participants (92 in each group). A mixed effects model with random coefficients will be used to assess the longitudinal effects of MICCO on changes in adjusted BMI z-score to minimize the effect of missing data. Logistic regression analysis will be used to assess the effect of the intervention on attrition. **Disparities (Aim 3):** The same models will be used to preliminarily assess the interaction between the intervention and race/ethnicity and insurance on adjusted BMI z-score and attrition to inform a larger multi-site trial that will be fully powered to evaluate disparities. Due to pilot nature of study and variability in engagement, the decision was made by the COBRE External Advisory Committee to end enrollment after 1 year.

C.6 POTENTIAL PROBLEMS, ALTERNATIVES. Analysis of EHR data suggests that it will be feasible to recruit the sample size intended and advertisement of the study through our community partners will also facilitate recruitment. However, if recruitment is slow we may expand eligibility to include children with BMI $\geq 85\%$ or from other Nemours clinics in rural areas. Every effort will be taken to refine MICCO based on input from stakeholders; if MICCO is found to be ineffective in the RCT, we will obtain qualitative feedback from our Councils, analyze app analytics, and assess whether behavior change improved. We understand that technology evolves quickly and modifications may be needed to ensure that the intervention remains current. We will leverage Nemours' investment in innovative technologies and the expertise of our IMPACT Core to continuously improve our intervention to be state of the art.⁵⁴ If families are experiencing connectivity issues, we may use primary care space and equipment for telehealth visits. Finally, success depends on effective collaboration with the community and therefore we will incorporate metrics to objectively measure collaborative efforts.²⁷

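### Practice is in neither the randomisation nor any planned model: a modest precision loss in Aim 2 and a possible, unshown contribution to Aim 3 interactions, both cheaply addressed in the analysis

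*Combined protocol and SAP*

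**What the plan says.** Under Aims 2 and 3, the participants are "patients of the primary care practices in Milford, Seaford, or Millsboro". Families, not practices, are the unit of randomisation, and allocation is made "using a 1:1 randomization scheme stratified by race/ethnicity", in three groups. No other stratum is named.

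Both arms have a local part. Standard care is in-person lifestyle counselling with the child's own PCP. In MICCO (C.3, Component 2), "Treatment will include biweekly telehealth or in-person (included based on parent and healthcare stakeholder feedback) visits" with the specialist team; telehealth runs through the app, and "in-person visits will be provided at Nemours Children's Health, Milford". The community health workers belong to each practice's medical home, and they refer families to services in their own zip code (C.3, Component 1).

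The analysis plan (C5) gives a mixed model with random coefficients for adjusted BMI z-score and a logistic regression for attrition. Neither names practice. For Aim 3, "The same models will be used to preliminarily assess the interaction between the intervention and race/ethnicity and insurance". C5 calls this preliminary and intended to inform a larger multi-site trial.

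**The concern.** Care in both arms can vary by practice: who gives the control counselling, how far a family travels for an in-person MICCO visit, and which local services are available. Attrition is non-attendance at the 6-month visit, so travel and visit mode plausibly matter. The Background (A.1) lists transportation among the barriers, and Preliminary Work (A.3) reports fewer no-shows for telehealth than for in-person visits.

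For Aim 2, leaving out a baseline factor that predicts the outcome gives up some precision and leaves chance imbalance unadjusted.

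For Aim 3, race/ethnicity and insurance are not randomised. Suppose that MICCO works differently at different practices and that the practices serve different mixes of families. An arm-by-race/ethnicity or arm-by-insurance interaction would then carry part of the practice difference. Stratifying the randomisation by race/ethnicity does not prevent this. Because Aim 3 feeds the design of a multi-site trial, readers should be able to see how far any interaction goes with practice.

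**Working it through.** **Inputs from the documents (C5):** 92 enrolled and 46 evaluable per arm, 50% attrition, a target difference of 0.25 z, 80% power, significance level 0.05; three practices (Aims 2 and 3). **Assumed, because the documents give no figures:** equal-sized practices (Milford share 1/3), the size of any practice difference, and the family mix by practice (Figure 5 is not shown).

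**1. The plan's own figures.** 92/(1 − 0.5) = 184 enrolled, as stated. No standard deviation (SD) is given, so the 46 per group cannot be confirmed. With a two-sided normal approximation it implies SD = 0.25/[(1.960 + 0.842) × √(2/46)] = 0.428, which is used below.

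**2. Chance imbalance in Milford share between arms.** The standard error (SE) is √(2 × 1/3 × 2/3 / n).
- n = 92 per arm: 0.070, a 95% range of ±13.6 points.
- n = 46 per arm: 0.098, a 95% range of ±19.3 points. This treats the retained families as a random half of those enrolled.

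**3. What that does to the Aim 2 estimates.** Assume that Milford differs from the other practices by 0.2 z.
- At the 95% limit, 184 families: 0.136 × 0.2 = 0.027 z, against a treatment SE of 0.428 × √(4/184) = 0.063.
- At the 95% limit, 92 families: 0.193 × 0.2 = 0.039 z, against 0.428 × √(4/92) = 0.089.
- Attrition, with an assumed 15-point difference between practices and a one-SE imbalance: 0.07 × 0.15 ≈ 0.01, or about 1 point, against a treatment SE of √(2 × 0.5 × 0.5/92) = 0.074.

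**4. Precision gained by adjusting.** If Milford differs from the others by D, the residual SD falls to √(0.428² − D² × 2/9). At 46 per group:

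| D (z) | Power after adjustment |
|---|---|
| 0 | 80% |
| 0.1 | 80.5% |
| 0.2 | 81.9% |
| 0.3 | 84.3% |

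**5. Aim 3.** The contribution of practice to an interaction is (difference in MICCO's effect, Milford versus other) × (difference in Milford share between groups). It is zero if either factor is zero.
- Attrition, on the risk-difference scale, with an effect 15 points larger at Milford and Milford shares of 50% and 25%: 0.15 × (0.50 − 0.25) = 0.0375, about 4 points. With three equal groups, 184/6 = 30.7 families per cell and 50% attrition, the interaction SE is √(4 × 0.25/30.7) = 0.18, or 18 points.
- BMI z-score, with an effect 0.2 z larger at Milford and shares of 50% and 20%: 0.2 × 0.30 = 0.06 z. Effect differences of 0.1 to 0.25 z and share differences of 0.1 to 0.4 give 0.01 to 0.10 z.

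**6. Simulation** (4,000 trials, randomisation balanced within race/ethnicity, Milford shares 50%/30%/20%, Milford outcome difference 0.2 z, MICCO effect 0.2 z larger at Milford). The Aim 2 estimate averages about −0.25 with or without practice (true value −0.25). The race/ethnicity interaction, which should be zero within practice, behaves as follows:

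| Families | Mean (SD), no practice terms | Mean (SD), practice and practice-by-arm added |
|---|---|---|
| 92 | −0.059 (0.220) | 0.003 (0.232) |
| 184 | −0.056 (0.154) | 0.003 (0.159) |

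**The case against.** The strongest reply is that the plan already narrows practice differences. Telehealth is open to every MICCO family, and primary care space may be used for it if connectivity fails (C.6). All PCPs get the same training, refreshers and handout. C.7 promises data on MICCO use and on the components of standard care visits, to account for variability. This carries weight, but the C.7 data arise after randomisation and cannot replace a baseline covariate. Practice is known for every child before allocation.

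A reader might infer that Milford families have an advantage in MICCO. The documents do not establish that. The team's own no-show data favour telehealth, practice is not the same as residence, and the location of the 6-month visit is not stated. The direction of any practice difference is open.

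A reader might also infer that an interaction explained by practice would be a false disparity. That goes too far. The project's stated goal (C1) is relevance and accessibility in order to reduce disparities. If one group benefits less because care is further away, that can be part of the disparity itself. Adjusting for practice-by-arm asks a different question, response net of local access, so it belongs beside the planned analysis and not in its place.

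Finally, this is a short grant narrative that names no covariates, not even the stratification factor. C.4 defers detail to a PHS Human Subjects form that was not available, and the part of the Approach between C1 and C.3 was not seen. A practice term could be specified in either place.

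**Conclusion.** The point holds as a minor improvement to the analysis plan. In the text available, practice is neither a stratum nor a model term, although delivery of both arms has a practice-level part.

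A reader might conclude that site differences bias the Aim 2 estimates. They do not do so systematically, because families are randomised individually and both arms draw on all three practices. The cost is noise. Under an assumed 0.2 z practice difference, chance imbalance at its 95% limit moves the estimate by less than half its standard error, and adjustment for differences of 0.1 to 0.3 z lifts power from 80% to between 80.5% and 84.3%.

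For Aim 3 the risk is conditional. It needs MICCO's effect and the racial/ethnic or insurance mix both to differ by practice, and the documents show neither. In the assumed examples the contribution (about 4 points on attrition, 0.06 z on BMI z-score) is well inside the sampling error of the interaction. These sizes rest on equal-sized practices or assumed Milford shares, an implied SD of 0.428 and invented practice differences, so they show scale only.

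**What to change.** - **Aim 2:** add primary care practice as a three-level fixed effect to the mixed model and the logistic model.
- **Aim 3:** keep the planned interaction models as the main analysis. Report beside them a sensitivity analysis that adds practice and practice-by-arm, so that readers can see how much of any interaction goes with practice and local access.
- **Reporting:** give the split of MICCO visits between in person and telehealth, by practice.
- **Randomisation:** no change. C5 records a decision to end enrolment after one year, so rebalancing on practice is probably too late to matter.

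**Cost:** a few lines in the analysis plan and a field already known for every child. Each Aim 2 model loses two degrees of freedom, or more if other rural clinics were opened as C.6 allows. The attrition odds ratio becomes conditional on practice instead of marginal, which should be stated when it is reported. The Aim 3 sensitivity analysis will have wide intervals. Practice by arm by race/ethnicity gives 3 × 2 × 3 = 18 cells, about 10 families each at 184 and 5 at 92, and fewer if enrolment closed short. The logistic version may therefore be sparse and should be labelled exploratory.

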Our research team has demonstrated the importance of addressing psychosocial determinants of health among families of children with obesity. The research project leader's (RPL) Academic Pediatric Association Research in Academic Pediatrics Initiative on Diversity Award study of children ages 4-12 years seeking treatment in the Nemours Weight Management Clinic found that families with moderate-high psychosocial risk, especially related to financial difficulties and caregiver and child mental health problems, were three times more likely to be lost to follow-up or not have a meaningful decrease in weight. Families who received psychological counseling were twice as likely to remain in obesity treatment.¹¹ Analyzing data on >7000 children in the National Health and Nutrition Examination Survey database, we found that children with severe obesity were two times more likely to be of a racial or ethnic minority backgrounds, from single-parent households, or from households experiencing poverty.³ Finally, in a survey of over 200 families of overweight children under age 5 from a Nemours primary care clinic, 85% endorsed one or more psychosocial needs.²¹ Our qualitative research,²² coupled with work by the Nemours Value Based Services Organization with 450 families across Delaware, led to the development of a 13-item literacy-sensitive, family-friendly psychosocial needs screener, incorporating items from validated measures and feedback from families.

Preliminary data from the RPL's K23 show that self-management tools keep families engaged in obesity treatment. Driven by our previous work demonstrating that parents with higher psychosocial risk report lower self-efficacy managing their child's behaviors,³⁶⁻³⁷ we developed and tested a video-based parenting intervention for families of children ages 4-12 with obesity.³² Qualitative interviews with caregivers produced three themes that informed design of the intervention and this proposed project: the value of hearing from other families of children with obesity of diverse backgrounds, the importance of choice and convenience in how the intervention is delivered, and the need to be activated. The intervention has been tested in a pilot RCT with 120 families attending the Nemours Healthy Weight and Wellness Clinic, with preliminary data showing improved short-term visit adherence among families who viewed the videos.

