Component 3: Self-Management Tools. Families will be provided with psychoeducational tools in English or Spanish through the Nemours App to promote lifestyle behavior change. These will include a self-monitoring tool (Figure 3) to track daily progress toward lifestyle behavior goals established during visits, a series of culturally-relevant videos developed by the research team to promote positive parenting among families of children with obesity (see A.3, Figure 4), and media-based educational resources (e.g., exercise/ cooking videos) to promote healthy lifestyle behaviors curated by multidisciplinary obesity specialists. Obesity specialists and community health workers will review data on an EHR dashboard about lifestyle behavior goal metrics and anthropometric measurements to inform clinical decisions during visits with families. Participants will also have the option of accessing the YMCA of Delaware's virtual platform through the App at no cost to participants.

Figure 4. Positive Parenting Videos

Figure 3. Goal Tracking

C.4 STUDY DESIGN: See PHS Human Subjects & Clinical Trials form for detailed eligibility criteria, sample size justification, recruitment/retention plan, time-line, human subjects protection, and data/safety monitoring. All participating

families will receive compensation for study visits, as detailed on the form.

AIM 1. REFINE MICCO WITH COMMUNITY ENGAGEMENT AND THINK ALOUD TESTING

COMMUNITY ENGAGEMENT

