Child Adiposity: Weight will be measured with a wireless smart scale that has been used in prior research and demonstrated excellent agreement with research-grade scales.⁴⁹⁻⁵⁰ Height will be measured using a reliable method used by RPL [name] and mentor [name] using a measuring tape and ruler, which has demonstrated validity when compared to measurement of height with a medical-grade stadiometer measured by a research team (Forset, et al., 2022).⁵¹ Procedures for ensuring reliability of measurements using these devices will be followed, per guidelines established by Krukowski and Ross during the pandemic.⁵⁰ Children will be measured by their caregiver each month in advance of visits, with weight measurements transmitted wirelessly to and height measurements entered into the Nemours App for the MICCO Group and measurements entered into the EHR by research staff for the Standard Care group.

Disparities: Child race/ethnicity and insurance (proxy measure of socioeconomic status) will be collected from the EHR. Age, sex, caregiver preferred language, and social needs (from screener) will also be collected.

C5. DATA ANALYTIC PLAN. **Think Aloud Testing (Aim 1):** Themes from qualitative interviews will be identified using an inductive thematic approach (see PHS Human Subjects Form for more detail).⁵³ **RCT (Aim 2):** Based on prior research describing the impact of behavioral interventions on BMI z-scores, we expect a mean difference in adjusted BMI z-score of 0.25 with the intervention, an effect size that has also been associated with a change in cardiometabolic risk.⁸ A sample size of 92 participants (46 in each group) can detect an effect size of this magnitude with a power of 80% and a level of significance of 0.05, assuming a 50% attrition rate based

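### With half the families expected to leave, the supplied text neither says that a month-6 home BMI is sought from those who stop attending nor tests the mixed model's missing-data assumption

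*Combined protocol and SAP*

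**What the plan says.** All places are in the combined protocol and SAP.

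- **Attrition.** Under Family Engagement in Treatment (Outcome Measures): "Attrition (non-attendance to 6 month follow-up visit) will be assessed via EHR review".
- **Sample size.** C5 doubles 92 evaluable children to 184, "assuming a 50% attrition rate based" on earlier studies. Families who leave are thus budgeted as lost to the BMI outcome.
- **Measurement.** Under Child Adiposity: "Children will be measured by their caregiver each month in advance of visits". The measurements are made at home in both arms.
- **Analysis.** C5 uses a random-coefficients mixed model for "changes in adjusted BMI z-score to minimize the effect of missing data". No missing-data assumption and no sensitivity analysis is stated.
- **Retention.** C.3, Component 2, says for MICCO that "providers will reach out to parents by their preferred method of communication (App, phone, or text) if a family misses a visit"; the listed content of that contact does not include weight or height. C.4 says that "families will receive compensation for study visits, as detailed on the form", and sends the reader to a PHS form for the "sample size justification, recruitment/retention plan, time-line, human subjects protection, and data/safety monitoring". That form was not supplied.
- **Enrolment.** C5 records a decision to stop enrolling after one year. It does not give the number reached.

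**The concern.** A likelihood-based mixed model uses each child's earlier monthly values and is valid when dropout depends on what has been observed. It cannot test that condition. With half the month-6 values expected to be missing, the estimate at month 6 leans heavily on it.

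Different attrition rates do not by themselves bias the model. Bias needs dropout to depend on weight change that was not observed, and it becomes material mainly when that dependence differs between arms. The documents give some reason to check. Attrition is an outcome that MICCO is meant to change, and outreach after missed visits is described only for MICCO. In the team's earlier clinic cohort (A.3), families at moderate to high psychosocial risk "were three times more likely to be lost to follow-up or not have a meaningful decrease in weight". That reads as a combined outcome. It suggests a shared risk factor, but does not show that dropout depends on weight or differs by arm.

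At stake is how far the trial's BMI effect can be relied on when it informs the larger trial that C5 has in view.

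**Working it through.** **1. The plan's own figure.** 92 / (1 − 0.50) = 184, or 92 per arm. This reproduces exactly.

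**2. Implied SD.** C5 gives a difference of 0.25, 80% power, a 0.05 level and 46 per arm, but no SD and no sidedness. For a two-sided t-test, 46 per arm gives 80% power at a standardised difference of 0.5905, so SD = 0.25 / 0.5905 = 0.423. The normal approximation gives 0.25 / [(1.960 + 0.842) × √(2/46)] = 0.428. I use 0.423 as the SD of 6-month change.

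**3. Illustrative model (assumed, not from the documents).**
- No true effect, 92 per arm, seven monthly measures (months 0 to 6), intercept SD 0.40, residual SD 0.08.
- Slope SD = √[(0.4234² − 2 × 0.08²) / 36] = 0.068 z per month.
- Effect = 6 × difference in slopes, by generalised least squares with known variances and a common baseline.
- Log-odds of dropout 0.5 to 1.0 per SD of slope; attrition 50% v 50%, or 30% v 50%. The plan gives only 50%.
- Dropout is either even (last measured month 0 to 5, equally likely) or early (months 0, 1, 2, 3 with probabilities 0.4, 0.3, 0.2, 0.1).

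**4. Bias in the 6-month effect (absolute, z).**

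| Dropout mechanism | Even | Early | False positives |
|---|---|---|---|
| Unrelated to slope, 30% v 50% | 0.002 | 0.000 | – |
| Same in both arms, 50% v 50% | up to 0.002 | up to 0.002 | 4% to 6% |
| Same in both arms, 30% v 50% | 0.004 to 0.008 | 0.014 to 0.026 | 4% to 6% |
| One arm only | 0.016 to 0.044 | 0.035 to 0.093 | 6% to 10% even; 8% to 25% early |

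In the one-arm case the sign depends on the arm. If children gaining weight leave only from MICCO, MICCO is flattered; if only from standard care, its benefit is understated. Over residual SDs of 0.03 to 0.15, the one-arm bias is 0.010 to 0.059 (even) and 0.025 to 0.113 (early), and the same-mechanism bias is at most 0.040. Estimating the variances by REML gave similar biases in the cases tried.

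**5. Tipping point.** Suppose the observed effect is 0.25 with 50% missing in each arm. A shift in one arm's dropouts moves the effect by 0.5 × shift, so the 95% CI reaches zero at shift = (0.25 − half-width) / 0.5, holding the half-width fixed.
- 92 per arm, half-widths 0.135 (even) and 0.150 (early): 0.115 / 0.5 = 0.23 and 0.100 / 0.5 = 0.20.
- 46 per arm enrolled (assumed), half-widths 0.191 and 0.213: 0.059 / 0.5 = 0.12 and 0.037 / 0.5 = 0.07.
- Simpler check with 46 completers per arm and no partial data: SE = 0.428 × √(2/46) = 0.089, 1.96 × SE = 0.175, and (0.25 − 0.175) / 0.5 = 0.15.
- The same shift in both arms at equal attrition cancels. At 30% v 50% with 92 per arm it would have to be (0.25 − 0.132) / 0.2 = 0.59 (even) or (0.25 − 0.144) / 0.2 = 0.53 (early).

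**6. Value of a month-6 measurement.** With dependence in standard care only and 50% v 50%, obtaining month 6 from a random half of dropouts cuts the bias from 0.024–0.042 to 0.010–0.020 (even) and from 0.054–0.091 to 0.022–0.039 (early).

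**The case against.** Four points can be made for the plan.

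- **Collection may already be covered.** The retention plan is in a form that was not supplied. The Child Adiposity text can also be read as scheduling a monthly value for every child whether or not visits are kept, with the visit wording describing timing only. This stands. The finding is that continued collection is not stated here, not that it is unplanned. Comparing the monthly measurement with the standard-care visit schedule does not settle it, because bimonthly can mean every two months or twice a month.
- **The primary model is standard.** This also stands; nothing here asks for it to be replaced.
- **Material bias needs a mechanism that no section documents.** Correct. The largest figures need one-arm dependence, log-odds of 1.0 per SD and many dropouts with a baseline value only. A reader might infer that 50% attrition, or unequal attrition, makes the BMI result biased. The benign rows of the table show that this does not follow.
- **It is a pilot and enrolment has ended.** The measurement step may be too late. The sensitivity analysis needs no new data and remains worth having, because the estimate is meant to inform a larger trial.

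A reader might also infer that power is safe because 184 already allows for the loss. The documents do not support that: enrolment was stopped after a year and the number reached is not given.

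**Conclusion.** The point holds as a recommended improvement, with medium confidence. The supplied text plans for half the families to be lost to the BMI outcome, does not say whether measurement outlasts attendance, and states no check on the assumption that carries the analysis.

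The size is conditional. It is negligible if dropout is unrelated to slope, or works alike in both arms at equal attrition. It is up to about 0.03 z if dropout works alike at 30% v 50%, and about 0.02 to 0.09 z if the dependence is confined to one arm. These figures rest on an SD solved from the sample size, assumed dropout mechanisms, a residual SD of 0.08 and 92 per arm. They illustrate the issue and do not estimate bias in this trial. The tolerance of the conclusion depends on actual enrolment, so the 0.20 to 0.23 z tipping point should not be quoted without that condition. The documents do not allow a statement that power is adequate.

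**What to change.** 1. **Measurement.** If follow-up is still open and the PHS form does not already say so, state under Child Adiposity that a month-6 home weight and height is requested from every randomised child in both arms, by the same contact procedure, whether or not visits were attended. If the form covers this, a cross-reference is enough.
2. **Analysis.** In C5, keep the planned mixed model, applied to all randomised children as allocated. Add a delta-adjusted (tipping-point) analysis: impute missing month-6 values from that model, shift them by 0 to 0.30 z separately by arm, at the number actually enrolled, and report the shift at which the conclusion changes.

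The cost is one reminder per family and one extra analysis. Response from disengaged families will be incomplete, so step 1 reduces bias without removing it. If follow-up is complete, only step 2 applies, and it should be labelled post hoc if added after the data have been seen.
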